8.6 Treatment Compliance

Compliance will be assessed by reviewing the subject's medication diary and study records as appropriate.

8.7 Storage, Stability, Labeling and Packaging

8.7.1 Storage and Stability

The study drug is stored at room temperature. Stability testing is ongoing.

8.7.2 Labeling and Packaging

The bulk drug and unit-dose containers will be labeled in accordance with national laws and regulations.

8.7.3 Blinding and Randomization

The trial will be conducted in double blinded, randomized manner with random assignment to standard of care plus brequinar or standard of care plus placebo. The brequinar and placebo capsules will be provided to each participating institution in pre-numbered bottles intended for individual subjects to be dispensed by the institution's pharmacist or designated person. Randomization assignments will be provided by an independent statistician to the drug packaging company. The pharmacist/designated person will dispense the next number in sequence to the next patient who qualifies for the study at an individual site.

8.7.4 Unblinding/Expectedness

Contact the Covance Medical Monitor if it is necessary to break the blind for this blinded study due to an adverse event (AE). Each site will be provided with a sealed envelope containing individual sealed envelopes for subject numbers assigned to that site. Each individual subject number sealed envelope will have the treatment (brequinar or placebo) randomly assigned to that subject number. Do not open the outer envelope or the individual sealed envelope unless it has been agreed with the Medical Monitor and the Sponsor that unblinding is necessary for that particular AE. Unblinding must be documented in the study records. Envelope seals are to be checked to ensure they remain intact during drug accountability monitoring.

If after a discussion with the Medical Monitor, the investigator or treating clinician believes the AE leading to unblinding to be related to the study drug, no further doses of drug should be administered to that subject.

Expectedness will be determined by establishing whether an adverse event is among those identified in the protocol and the brequinar IB or are commonly associated with COVID-19 or similar severe viral illnesses and their complications.

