8.4.2 Study-Level Stopping Criteria

Study enrollment is to be paused if any of the below criteria are met:

- If ≥ 3 subjects develop the same related Grade 4 (life-threatening) adverse event or laboratory abnormality;
- If ≥ 5 subjects develop the same related Grade 3 or 4 adverse event or laboratory abnormality;
- If ≥ 10 subjects develop any related Grade 3 or 4 adverse event or laboratory abnormality.

Following assessment by the Data Monitoring Committee (DMC, see [Section 10.9](#)), the DMC will determine whether to stop the study, amend the protocol, or continue the study per protocol.

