8.7.5 Study Drug Accountability

The study drug provided is for use only as directed in this protocol.

The Investigator must keep a record of all study medication received, administered, and discarded. It must be clear from the records whether the subject received study medication and what subject number was assigned to which subject. Adequate drug is to be dispensed for the number of subjects expected to be treated at each institution.

The pharmacist/staff member responsible for drug accountability is to document the date and time of dispensing and for what subject the study drug was intended (i.e., record subject initials and birth date or other unique identifier). A pharmacy manual will be provided by the Sponsor.

At the end of the study any unused study drug will be returned to the Sponsor for destruction or may be destroyed locally; disposition of study drug will be documented.

The Sponsor will be permitted access to the trial supplies at any time within usual business hours and with appropriate notice during or after completion of the study to perform drug accountability reconciliation. Records may be electronic or paper and may be accessed remotely for monitoring/drug accountability purposes.

Each subject will be provided with one bottle with five brequinar or five placebo capsules for the five days of dosing.

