13.3 Data Monitoring

Suitably qualified and trained clinical research personnel of the Sponsor will visit the trial site or will access the electronic health record (EHR) or conduct remote monitoring visits at regular intervals during the trial for monitoring purposes and to assist the research staff with any queries. CRFs and source documentation will be available for review during monitoring visits to the trial site. The function of this monitoring is to ensure compliance with the protocol, adherence to regulatory and GCP obligations, proper maintenance of records including IP accountability records, correct administration of IP including storage conditions and accurate reporting of AEs. On-site visits are not required for any monitoring visits for this study.

Once the data from the case report forms have been entered onto the database, they will be reviewed, and the data verified against the subject's source data. Any discrepancies will be tracked by paper or electronically with an electronic audit trail.

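### Protocol 8.7.4 does not require severity and causality to be recorded before a subject's code is opened, and gives no emergency route around the two approvals needed to open it

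*Protocol*

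**What the plan says.** All protocol references are to version 5.0.

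- **Where the codes are (8.7.4).** "Each site will be provided with a sealed envelope containing individual sealed envelopes for subject numbers assigned to that site"
- **Who may open one (8.7.4).** "Do not open the outer envelope or the individual sealed envelope unless it has been agreed with the Medical Monitor and the Sponsor". What must be agreed is that unblinding is needed for that particular AE. A code break has to be documented. No exception for an emergency is written.
- **Causality (8.7.4).** The next paragraph covers the case where, following a discussion with the Medical Monitor, "the investigator or treating clinician believes the AE leading to unblinding to be related to the study drug"; dosing of that subject then ends. The section does not say when severity and causality are to be entered relative to opening the envelope.
- **What relatedness drives.** Section 10.3 makes it the investigator's call. All three pause rules in 8.4.2 count related events; the second, for example, is met when at least five "subjects develop the same related Grade 3 or 4 adverse event or laboratory abnormality". Relatedness also enters the individual Grade 3 rule (8.4.1), the SUSAR definition (10.6) and the drug-related AE tables (SAP 7.7.2).
- **Seals.** Section 8.7.4 says: "Envelope seals are to be checked to ensure they remain intact during drug accountability monitoring". Under 8.7.5, accountability records "may be accessed remotely for monitoring/drug accountability purposes". Section 13.3 adds: "On-site visits are not required for any monitoring visits for this study". Section 12.4, however, says Sponsor personnel will visit the site regularly.

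**The concern.** An investigator who has just learned a subject's treatment is no longer a blinded judge of whether the event is related. Seeing placebo is a reason to answer no, and seeing brequinar is a reason to answer yes. In the SAP 7.7.2 drug-related tables, both shifts widen the apparent gap between the arms. In the 8.4.2 counts, which do not distinguish the arms, a placebo event can drop out and a doubtful brequinar event can be added, so the net direction is not known in advance.

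The second matter is separate. Subjects are out-patients followed largely by telephone and telemedicine. If treatment knowledge is needed urgently, the site must first obtain agreement from two other parties, and the protocol does not say what happens if either cannot be reached. The rule also makes the Sponsor a party to every single-subject decision to unblind.

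**Working it through.** The plan states no figure on this point, so there is nothing to reproduce. The check is mainly textual, with one illustration of how sensitive a pause rule is to the related label.

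**1. Order of steps.** Section 8.7.4 gives this sequence: contact the Medical Monitor, obtain both agreements, open, document. The belief about relatedness comes after a discussion with the Medical Monitor, but is not placed before or after opening. Section 10 lists relationship among the AE details to record, and 10.5 requires SAEs to be reported within 24 hours; neither is tied to a code break. SAP 7.7.2 uses the recorded relationship without separating pre-break from post-break entries. A site that enters causality before opening complies, and so does one that enters it afterwards.

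**2. Emergency access.** The ban in 8.7.4 covers both the outer and the individual envelope and depends on both agreements. No other section of version 5.0 supplies an exception.

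**3. Sensitivity of the ten-subject pause rule (any related Grade 3 or 4).** Assumptions, not taken from the documents: each of *n* subjects independently has such an event with probability *p*, and a share *q* of these events is relabelled unrelated. The number counted is then binomial with parameters *n* and *p*(1 − *q*), and the rule is met with probability P(X ≥ 10). For *n* = 100:

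| *p* | *q* = 0 | *q* = 10% | *q* = 20% | *q* = 30% |
|---|---|---|---|---|
| 10% | 0.549 | 0.412 | 0.278 | 0.162 |
| 15% | 0.945 | 0.883 | 0.774 | 0.613 |
| 20% | 0.998 | 0.991 | 0.968 | 0.908 |

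At *p* = 10%, the expected count is 100 × 0.10 = 10, so *q* = 10% means about one relabelled subject and *q* = 30% about three. If only 50 subjects can contribute, moving *q* from 0 to 10% changes the probability from 0.025 to 0.013 at *p* = 10%, and from 0.209 to 0.129 at *p* = 15%. The rule is sensitive when the true rate puts the expected count near the threshold, and much less so elsewhere.

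**4. Limits of the illustration.** Only a subject whose code has been opened can be relabelled because of the envelope, and the documents give no expected number of code breaks, so *q* is unknown. The model also relabels downward only; upward shifts in brequinar subjects would offset it.

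**5. Seals.** The check in 8.7.4 is required, but it is attached to an activity that 8.7.5 and 13.3 allow to be remote, and no remote method is described. Section 12.4 (regular site visits) and section 13.3 (on-site visits not required) do not agree.

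**The case against.** A reader might infer four stronger points. The documents do not support them.

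- **That the protocol places the causality judgement after opening.** It does not. Contact with the Medical Monitor comes first, and the sentence about relatedness governs further dosing. What stands is that no blinded assessment has to be on record before the break.
- **That the two-approval rule endangers the blind.** It restricts opening and so protects the blind. What stands is the missing emergency route.
- **That nobody has to look at the seals.** Section 8.7.4 requires the check, 12.4 foresees site visits, 8.7.5 gives the Sponsor access to supplies, and its remote-access sentence concerns records. A pharmacy manual, not among the documents here, may say more. What stands is that the method under remote monitoring is unspecified.
- **That one relabelled event is plainly material.** Section 8.2.1 reports 2/39 = 5.1% with a related Grade 3 or 4 AE, or 50 × 2/39 ≈ 2.6 expected in the brequinar arm. These are events of any type, so they compare with the ten-subject trigger. The three- and five-subject triggers need the same event. At the 5.1% rate, P(X ≥ 10) is 0.033 even with 100 subjects.

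There are also safeguards. The DMC reviews all AEs and compares the arms (10.9). The individual Grade 4 rule ignores relatedness (8.4.1). Suspension for haematologic toxicity under 10.8 is not worded in terms of relatedness. Missing causality counts as related (SAP 6.2). SAP 7.7.2 also tabulates all AEs, all Grade 3 or higher AEs and all SAEs. The primary endpoint is a central-laboratory viral load. Finally, removing a true placebo event from a toxicity count removes an event that brequinar did not cause. These points limit the consequence. They do not supply the missing record: the scheduled DMC reviews come after 20 and 40 subjects complete Day 8, and the 8.4.2 counts still depend on the label.

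**Conclusion.** The point holds as two procedural defects in 8.7.4, plus one clarification. First, causality and severity may be judged with knowledge of treatment, and that judgement then enters the 8.4.2 counts, SUSAR classification and the drug-related tables. Second, no code can be opened in an emergency without two agreements; this concerns access and patient safety. The clarification is how seals are verified when monitoring is remote.

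The size of any bias cannot be established. It reaches only code-broken subjects, their number is not given, and review of all AEs by the DMC limits the effect. The probabilities above rest on assumed event rates and relabelling shares, and show sensitivity only. A conclusion that the blind is insecure is not supported. The changes are still worth making, because they are cheap and remove an avoidable route to bias.

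**What to change.** In protocol 8.7.4:

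- **(a) Record first.** Require a time-stamped severity and causality entry before any envelope is opened. If an emergency prevents this, require an entry flagged as made after the break. Use the pre-break assessment for the 8.4.2 counts and the SAP 7.7.2 tables, with a matching sentence in the SAP. It would also be on file for SUSAR classification.
- **(b) Emergency route.** Add a code-break route for the single subject that does not wait for both approvals, with prompt notification of the Medical Monitor and no disclosure of the treatment to the Sponsor's study team.

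As a secondary clarification, reconcile sections 12.4 and 13.3 on site visits, and state how seals are verified, and envelopes reconciled before the data are unblinded, when monitoring is remote.

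The cost is wording in 8.7.4, the monitoring sections and the SAP, slightly more site paperwork, and possibly one or two extra single-subject code breaks. No dose or treatment rule changes.

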8.7.5 Study Drug Accountability

The study drug provided is for use only as directed in this protocol.

The Investigator must keep a record of all study medication received, administered, and discarded. It must be clear from the records whether the subject received study medication and what subject number was assigned to which subject. Adequate drug is to be dispensed for the number of subjects expected to be treated at each institution.

The pharmacist/staff member responsible for drug accountability is to document the date and time of dispensing and for what subject the study drug was intended (i.e., record subject initials and birth date or other unique identifier). A pharmacy manual will be provided by the Sponsor.

At the end of the study any unused study drug will be returned to the Sponsor for destruction or may be destroyed locally; disposition of study drug will be documented.

The Sponsor will be permitted access to the trial supplies at any time within usual business hours and with appropriate notice during or after completion of the study to perform drug accountability reconciliation. Records may be electronic or paper and may be accessed remotely for monitoring/drug accountability purposes.

Each subject will be provided with one bottle with five brequinar or five placebo capsules for the five days of dosing.

8.8 Prohibited Medications

Treatment is prohibited with another DHODH inhibitor (e.g., leflunomide and teriflunomide). Treatment is prohibited with agents known to cause bone marrow suppression leading to thrombocytopenia.

8.9 Study Adjustments Due to COVID-19

Due to the highly contagious nature of COVID-19, multiple adjustments and revised procedures are rapidly evolving regarding clinical trial management and study conduct. Reasonable procedures implemented by study staff to avoid spreading this disease are acceptable to Clear Creek with written permission. Examples include but are not limited to e-consent, telephone consent and study visits conducted by telemedicine, telephone or other digital media.

Background standard of care is to be maintained in both treatment arms. The standard of care is expected to change as additional information, such as that from randomized controlled trials, emerges, and the Sponsor and the treating clinicians will need to address anticipated off-label use of any other drugs, devices, or interventions that might be used to manage COVID-19 (e.g. anticoagulants).

The Sponsor and treating clinicians are to consider changes in SOC over time, for example, overlapping toxicities of brequinar and a SOC treatment expected to be widely used is to be considered. The availability of new standard of care treatment may change over time and vary from one clinical trial site to another. The Sponsor will discuss these issues with FDA should the need arise.

9 CONDUCT OF THE TRIAL

9.1 Ethical and Regulatory Considerations

The trial will be performed in accordance with the Declaration of Helsinki (1964) as revised in Tokyo (1975), Venice (1983), Hong Kong (1989), South Africa (1996), Scotland (2000, Note of Clarification 2002 & 2004) and Seoul 2008 (Appendix A), and Fortaleza (Brazil) (2013), and with the International Council on Harmonization (ICH) Tripartite Guideline on Good Clinical Practice (CPMP/ICH/135/95, Jan.97) and United States (US) FDA Regulations.

9.2 Informed Consent

The principles of informed consent in the current edition of the Declaration of Helsinki must be implemented in each clinical study before protocol-specified procedures are carried out. Informed consent must be obtained in accordance with US Code of Federal Regulations (21 CFR Part 50), the FDA Guidance on Conduct of Clinical Trials of Medical Products during the COVID-19 Public Health Emergency (March 2020, Updated April 16, 2020) [\[20\]](#), as well as local and national regulations. Information should be given in both oral and written form whenever possible and deemed appropriate by the Institutional Review Board (IRB). Subjects and their relatives, if necessary, must be given ample opportunity to inquire about details of the study.

The Investigator or qualified designated person will verbally inform subjects as to the nature, expected duration and purpose of the trial, the administration of the Investigational Product (IP), and the hazards involved, as well as the potential benefits that may come from treatment with this IP. The trial procedures will be explained in lay language and any questions will be answered. The subjects will be given an IRB-approved consent form. The subjects will be given appropriate time to consider their participation in the trial and have any questions answered prior to signing the consent form. If a subject agrees to participate, he/she will sign and date an informed consent form and be provided with a copy of the signed consent. All subjects who sign an informed consent form are to be recorded on the applicable screening log. If the subject is unable to consent for any reason, a designated family member or healthcare power of attorney or other person may consent per institutional policy.

The subject will be informed that his/her medical records will be subject to review by the Sponsor, Sponsor's representatives, and possibly by a representative of the FDA and other relevant regulatory authorities. Subjects will be informed that they are free to refuse participation in this clinical investigation, and if they should participate, it will be made clear to them that they may withdraw from the trial at any time without prejudicing further medical care they may require. The subject will receive a copy of the consent form as well as an information sheet about the trial.

Informed consent must be obtained from every subject prior to any study-specific procedures. Standard procedures carried out prior to completing the informed consent process but within the time constraints of the protocol may be used for baseline evaluation; they need not be repeated. Documentation of consent will be subject to review by the Sponsor; if in writing, a copy will be given to the subject and a copy will be filed with the subject's medical notes. Verbal consents will be documented by the study team as appropriate and agreed by the IRB.

Note that informed consent procedures have been affected by COVID-19, and the study staff may use any consent method that has been approved by the IRB (e.g., phone consent, verbal consent with

witness, e-consent, etc.) of the local institution. In-person consent, written consent signatures and providing hard copies to the subject are examples of procedures that may be foregone under these circumstances.

The study should be discussed with the potential participant only after an initial review of his/her clinical status and appropriateness for participation have been evaluated to determine if he/she meets the subject selection criteria.

A sample subject information sheet and consent form are available from Clear Creek. The final version at each institution may differ depending on institutional requirements and standard formats. This protocol will not be amended for site specific changes as such changes are to be made to the site's consent when required.

9.3 Institutional Review Board

It is the responsibility of the Investigator to submit the protocol, consent form and information sheet to the IRB. An IB will be available for review by the IRB. The protocol and informed consent form (ICF) must be approved by the IRB prior to the recruitment of the first subject. The template consent form may be revised in accordance with site-specific requirements with Sponsor review and approval. A copy of the IRB written approval must be provided to the Sponsor and investigator before the trial may start at that institution. Written approval from the IRB is also required for substantial protocol amendments prior to their implementation.

A substantial amendment may arise from changes to the protocol or from new information relating to the scientific documents in support of the trial. Amendments are “substantial” when they are likely to have an impact on:

- the safety or physical or mental integrity of the subjects;
- the scientific value of the trial;
- the conduct or management of the trial; or
- the quality or safety of any IP used in the trial.

If it is necessary to change or deviate from the protocol to eliminate an immediate hazard to the subjects, the Investigator will notify the Sponsor and the IRB of the new events and the measures taken as soon as possible.

The Investigator will report promptly to the Sponsor and IRB any new information that may adversely affect the safety of the subjects or the conduct of the trial. On completion of the trial, the Investigator will inform the applicable IRB as per local IRB requirements that the trial has ended. If the study is terminated for any reason, the investigator will return all clinical supplies and study-related equipment supplied by the Sponsor to the Sponsor unless otherwise specified.

9.4 Schedule of Events

Study activities will be conducted or supervised by experienced personnel throughout the study based on the Schedule of Events. The subjects may self-collect the saliva sample for viral load testing and perform other study activities such as body temperature, heart rate, respiratory rate, SpO₂, and

symptom assessments themselves with appropriate training. Equipment will be provided to the subject for study purposes including a pulse oximeter with heart rate monitoring capability and a thermometer. Telemedicine visits such as phone calls or other remote media are to be utilized as much as possible. Subjects may need to come to an out-patient facility or be visited by a home health professional for some study assessments.

See [15.1 Schedule of Events in Appendix A](#) for the full list of study assessments and timings.

Blood chemistry tests include blood urea nitrogen (BUN), creatinine, alkaline phosphatase (ALK), alanine amino transferase (ALT), aspartate amino transferase (AST), total bilirubin, total protein, albumin, glucose, serum electrolytes (sodium, potassium, chloride, carbon dioxide/bicarbonate, calcium, lactate dehydrogenase (LDH), and C-reactive protein (CRP). Chemistry samples may be banked for future analyses.

Hematology tests include hemoglobin, hematocrit, complete blood count with full differential, and platelet count.

Viral load sampling is to be carried out on Days 1, 4, 8, 12, 15, 22, and 29. The subject is to self-collect saliva samples with appropriate training for this analysis. Samples may be banked for future analyses. The subject must have a documented positive SARS-CoV-2 result to be eligible for Screening. Eligible subjects must have symptom(s) consistent with SARS-CoV-2 infection at time of randomization in the opinion of the investigator and onset of first COVID-19 symptom must be ≤ 7 days prior to first dose.

Safety laboratory results (chemistry and hematology) are to be reviewed by investigator or designated site personnel within 48 hours of receipt of results.

Hospitalization status after enrollment is to be recorded as not hospitalized or admitted to hospital as an in-patient with admission > 24 hours.

As much of the study as possible will be conducted via telemedicine remote from the site (e.g., consent, medical history, concomitant medications may be collected remotely). Subjects will be visited at home (or place of residence) by a home health nurse or come to the site for an in-person visit at Screening and on study Day 1. The subjects will be visited at home for Study Days 8, 15, and 29. On study Days 4, 12, and 22 the vital signs and saliva collections will be observed via telemedicine by the study site staff. Site staff will have a telephone call with subjects on study days 2, 3, 5, 6, and 7 to assess changes in concomitant medications and to assess adverse events, especially those that may indicate thrombocytopenia, e.g., unusual bruising, epistaxis, gingival bleeding, etc., and mucositis. Subjects will be provided with a pulse oximeter and thermometer during the Screening or Day 1 visit, as well as being trained on the use of these devices during the visit. Training will also be provided for the saliva collection required for viral load testing. Assessments will be recorded by the study staff during home and clinic visits and by the site staff during telemedicine visits. These data will be entered in the eCRF by the site staff or as determined by the study team.

